## 7.2 Covariates and Subgroups

The covariates that are recorded at baseline are:

- Demographics (age, sex, weight, family history of allergy)
- Other allergic diseases (asthma, eczema, rhinitis)
- Sensitisation to tree nuts
- Severity of worst reaction before enrolment (WAO score)
- DBPCFC – WAO score, LOAEL, NOAEL
- Peanut SPT wheal diameter
- Other nut SPT wheal diameter
- Peanut specific IgE
- Total IgE
- Basophil AUC of CD63MFI against peanut protein concentration
- Basophil AUC of %CD63 positive cells against peanut protein concentration
- Tryptase
- QoL score

## 7.3 Missing Data

The frequency of missing data for all variables used in analysis will be summarised in a table.

To avoid using only complete case data for regression analysis when baseline covariates are missing, the ‘missing indicator’ method will be used. That is, we will include a binary indicator variable for the missingness of each covariate in regression models and we will ‘fill in’ all missing baseline covariate values with a fixed arbitrary number, say 0, to avoid software programs automatically omitting non complete cases from analysis.

[figure not shown]
## 8 Summary of Study Data

Summaries of the study data will be presented as tables with separate columns for randomised group. All randomised patients will be included regardless of those who may not have completed the study. A table of baseline characteristics of patients will be included with a row for each covariate described in section 7.2.

Continuous variables will be summarised using means and standard deviations (or median and interquartile range if more appropriate) and categorical variables will be summarised using frequencies and percentages. The extent of missing data will be reported using annotations for the table and graphically using plots

### 8.1 Subject Disposition

Below is a blank example of a CONSORT diagram to include in the final report

### 8.2 Protocol Deviations

The summary statistics will be produced in accordance with section 8.

### **8.3 Demographic and Baseline Variables**

The summary statistics will be produced in accordance with section 8.

### **8.4 Concurrent Illnesses and Medical Conditions**

The summary statistics will be produced in accordance with section 8.

### **8.5 Prior and Concurrent Medications**

The summary statistics will be produced in accordance with section 8.

### **8.6 Treatment Compliance**

The summary statistics will be produced in accordance with section 8.

## **9 Efficacy Analyses**

All statistical tests described in this section use a 2-sided 5% significance level. Non-parametric tests may be used instead of parametric tests if the assumptions are not appropriate. Sensible transformations of data may be used to allow the data to fulfil assumptions.

Plots (e.g. histograms, residuals) will be used to assess the assumptions and fits of regression models.

Tests will be accompanied with a measure of effect size (e.g. difference, odds ratio etc.) and a 95% confidence interval.

All analyses will be performed on an intention to treat (ITT) basis.

### **9.1 Primary Efficacy Analysis**

Fisher's exact test will be used to compare the incidence with desensitisation to peanut after 6 months between the intervention and waiting list group.

Multiple logistic regression will be used to adjust the odds of desensitisation for baseline characteristics described in section 7.2.

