## 5.3 Randomisation and Blinding

Subjects were allocated using minimisation to avoid imbalance of confounding factors between groups, with a random element using a weighting probability of 0.8 – i.e. patients were allocated to the group which would provide optimal balance with 80% probability.

The minimising variables were age (7–<12, 12–15), sex, allergy severity (mild, moderate, severe, never eaten), asthma, serum peanut IgE ( $\leq 28$ ku/l,  $>28$ ku/l), challenge threshold ( $>5$ mg, 50–200mg,  $>200$ mg) and other current food allergies.

Patients are not blinded to their randomised groups. However the primary outcome will be assessed using a double blind placebo controlled food challenge (DBPCFC). On the challenge neither the investigator, nurse nor the participant will know whether the participants dose is peanut or placebo.

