## 6 Sample Size

Based on Fisher's exact test with 90% power and 5% significance (two-sided) a sample size of 49 in each group is sufficient to detect proportions of participants with desensitisation to peanut of 64% and 30% in the intervention and control group respectively. Allowing for 5% drop out increases the sample size to 52 participants in each group and 104 subjects overall.

Based on the above we would expect 35 waiting list group patients to proceed to the active intervention in phase 2. To confirm efficacy of immunotherapy the success rate of all participants (intervention and phase 2 waiting list) should be within 10% of the success rate seen in intervention participants alone in phase 1.

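### The primary Fisher's exact test is valid and adequately powered, but it uses none of the minimisation factors and so gives up some power that a short adjusted analysis would recover at little cost.

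*SAP*

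**What the plan says.** - **Allocation (SAP 5.3).** "Subjects were allocated using minimisation to avoid imbalance of confounding factors between groups", with probability 0.8 of assignment to the balancing arm. The seven factors are age, sex, allergy severity, asthma, peanut IgE, challenge threshold and other current food allergies.
- **Primary test (SAP 9.1).** "Fisher's exact test will be used to compare the incidence with desensitisation to peanut after 6 months between the intervention and waiting list group". Table 2.1 lists Fisher's test as the formal analysis.
- **Adjusted model (SAP 9.1).** The next sentence adds: "Multiple logistic regression will be used to adjust the odds of desensitisation for baseline characteristics described in section 7.2". Section 9.1 does not say which of the two analyses decides the trial. Section 7.2 is a long list that includes "DBPCFC – WAO score, LOAEL, NOAEL". Table 2.2 narrows it to 13 covariates plus treatment. That set covers age, sex, asthma, peanut IgE and baseline NOAEL, but not allergy severity or other food allergies.
- **Level (SAP 9).** "All statistical tests described in this section use a 2-sided 5% significance level".
- **Sample size (SAP 6).** "Based on Fisher's exact test with 90% power and 5% significance (two-sided) a sample size of 49 in each group is sufficient". The planned rates are 64% with intervention and 30% in controls, and a 5% dropout allowance brings the target to 52 per arm, or 104 in total.

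Because the sample size and Table 2.1 both rest on Fisher's test, it is naturally read as the deciding analysis.

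**The concern.** Fisher's test treats every split of participants with the same margins as equally likely. Minimisation makes splits that are unbalanced on the chosen factors rare. If those factors predict the outcome, the test allows for chance imbalance that the design has largely removed, and its true size falls further below 5%. Challenge threshold is the baseline form of the quantity behind the primary endpoint, so it may well be prognostic, although the SAP gives no figure for this.

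At stake is efficiency: a larger p-value and a wider interval than the design could support. This matters most if the true effect is smaller than the planned 34 points. The data needed for adjustment are all collected at week 0.

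**Working it through.** **Inputs from the SAP.** Fisher's exact test, two-sided 5%, 64% v 30%, 49 per arm (98 in all), 5% dropout (Section 6); minimisation on seven factors with probability 0.8 (Section 5.3). **Assumed, because the SAP does not give them:** the distributions of the factors, and their prognostic strength, expressed as the SD of the log-odds that they contribute and varied from 0 to 1.4.

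**1. Reproducing the plan's figure.** Power is the sum of Bin(a; n, 0.64) × Bin(b; n, 0.30) over all tables (a, b) with Fisher p ≤ 0.05. It is 89.6% at 48 per arm, 90.6% at 49 and 93.2% at 52. Dropout: 49/0.95 = 51.6, rounded up to 52. The plan's figures reproduce. The uncorrected formula

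n = [1.96√(2 × 0.47 × 0.53) + 1.2816√(0.64 × 0.36 + 0.30 × 0.70)]² / 0.34² = 43.2, so 44 per arm,

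shows that the 49 already pays for Fisher's conservatism.

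**2. Size from discreteness alone.** The same sum with equal rates at 49 per arm gives 3.0% at a common rate of 30% and 3.3% at 47%, which is also the maximum to one decimal. At 52 per arm the maximum is 3.9%. Boschloo's test, which keeps its size below 5%, has power 92.9% at 49 per arm. So 92.9 − 90.6 = 2.3 points are lost before minimisation enters. Exactly equal arms are an unfavourable case: the same enumeration at 50 v 48 gives size 3.9% (30%) and 4.2% (47%), and power 92.5%. Minimisation does not force exact equality.

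**3. Under minimisation.** Simulation with N = 98, seven factors and probability 0.8, 3000 runs per cell. Fisher's test is compared with a linear risk difference adjusted for threshold, IgE, age and sex with HC3 standard errors.

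| Assumed SD of log-odds | Null rejection, Fisher / adjusted | Power 64% v 30% | Power 55% v 30% |
|---|---|---|---|
| 0 | 3.3% / 4.4% | 91.3% / 91.8% (+0.5) | 66% / 67% (+1) |
| 0.7 | 2.7% / 4.1% | 91.2% / 93.8% (+2.6) | 66% / 73% (+7) |
| 1.05 | 2.6% / 4.3% | 92.3% / 95.6% (+3.3) | 68% / 78% (+10) |
| 1.4 | 2.5% / 4.2% | 92.1% / 97.4% (+5.3) | 67% / 81% (+14) |

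A separate run of the same design gave Fisher size 2.3–3.1% and adjusted size 3.6–4.2%, with gains of about 1–4 points at 64% and 2–13 points at 55%. Monte Carlo standard errors are about √(0.03 × 0.97/3000) = 0.3 points on size, 0.5 points on power near 92% and 0.9 points near 67%. The two runs therefore agree within error.

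**4. Ordinary logistic regression as the alternative.** At N = 98, a likelihood-ratio test adjusted for all seven factors rejected 6.2–6.8% under the null (common rate 47%). Adjusted for threshold and IgE only, it rejected 5.2–6.3%. With the critical value raised to restore 5%, the two-covariate version gained 0.7, 1.9, 3.5, 4.4 and 4.6 points over Fisher's at SD 0, 0.35, 0.7, 1.05 and 1.4, in line with step 3.

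**5. Load on the planned model.** Expected desensitised participants are 49 × 0.64 + 49 × 0.30 = 46. Table 2.2 puts 13 covariates plus treatment on these, before the missing-data indicators of Section 7.3.

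**The case against.** The strongest reply is that nothing stated in the plan is wrong. The sample size was computed for the test that is used, its power is met at 49 per arm and exceeded at 52, and type I error is protected. That stands in full.

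A reader might infer that the 5% level in Section 9 is misstated. It is not: a significance level is an upper bound, and a test with true size of 2–3% respects it. A reader might also infer that the trial is underpowered, or that minimisation costs a firm 4–6 points. The SAP does not support this. It gives no correlation between baseline and outcome. A 6-point figure appears only if a variance formula with an assumed correlation of 0.5 (96.6%) is set against Fisher's power under simple randomisation (90.6%), which is not this design. Simulated under minimisation at that correlation, the figures are 97.9% v 93.5%, or 4.4 points. Part of the loss is also discreteness and has nothing to do with covariates.

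It can fairly be said that Section 9.1 already plans an adjusted model that includes baseline NOAEL. But that model is not named as decisive. Its covariate set differs between Section 7.2 and Table 2.2, Table 2.2 omits two minimisation factors, and the simulated seven-factor logistic test did not hold 5%. It does not fill the gap.

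Finally, adjustment replaces an exact p-value with a model-based one, and the short set leaves out three minimisation factors. Both are true. The HC3 test stayed below 5% in every null setting tried, and a re-randomisation p-value would respect all seven factors.

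**Conclusion.** The point holds as a matter of efficiency. The natural deciding test ignores the factors on which the design was balanced. It is valid and reaches its stated power, but it runs at about 3.0–3.3% at 49 per arm from discreteness alone, and at about 2–3% under minimisation if the factors are prognostic. Against a size-controlled adjusted test it forgoes about 0–5 points of power at the planned 64% v 30%, and about 2–14 points at 55% v 30%. The lower ends apply when the factors carry little or no prognostic information. The 55% rate, the prognostic strengths and the factor distributions are assumptions and not figures from the SAP. No bias and no excess false-positive risk is shown. This is a cheap improvement.

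**What to change.** Before outcomes are analysed, amend Section 9.1 and Table 2.1 as follows.

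- State that the deciding analysis is the treatment risk difference adjusted for log baseline LOAEL, log peanut IgE, age and sex, with LOAEL, IgE and age kept continuous. LOAEL suits a log scale because entry requires a positive challenge, so it is above zero for everyone.
- Use a small-sample robust (HC3) standard error, or a re-randomisation p-value for the same statistic obtained by re-running the 0.8 minimisation.
- Do not use an ordinary logistic likelihood-ratio test on all factors as the deciding test.
- Keep Fisher's exact test as the supportive unadjusted analysis, and give the Table 2.2 model a supportive role.

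The sample size in Section 6 can stay. The cost is SAP wording and a few lines of code, with no new data and no more participants. The small downside is a primary p-value that is model-based rather than exact, unless the re-randomisation version is chosen. Section 5.3 describes allocation in the past tense and participants are not blinded, so the change should be dated and recorded as made before the outcome data were examined.

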### 13.1 Tables

Table Title	No.	Population	Endpoint	Time Points or how to conglomerate	Covariates or Subgroups	Summary Statistics	Formal Analysis
Summary of patient characteristics	1.1	Full analysis	Age	Baseline	Treatment	n, mean, SD	NA
			Sex			n, %	
			Weight			n, mean, SD	
			Asthma			n, %	
			Eczema			n, %	
			Rhinitis			n, %	
			Other food allergy			n, %	
			Tryptase			n, mean, SD	
			WAO score (historical)			n, median, range	
			Sensitisation to tree nuts			n, %	
			QoL score			n, median, range	
			Peanut specific IgE			n, median, range	
			Total IgE			n, median, range	
			Peanut SPT wheal diameter			n, mean, SD	
			Other nut SPT wheal diameter			n, mean, SD	
			Family history of peanut allergy			n, %	
			DBPCFC total peanut protein consumed			n, median, range	
DBPCFC peanut threshold (NOEL)	n, mean, SD						
DBPCFC WAO score	n, median, range						
DBPCFC LOAEL	n, mean, SD						

Basophil AUC of CD63MFI  
against peanut protein  
concentration

n, mean , SD

Basophil AUC of %CD63 positive  
cells against peanut protein  
concentration

n, mean, SD

Desensitisation to peanut after 6 months	2.1	Full analysis	Allergy desensitised or undesensitised	6 months	Treatment	n, %, odds ratio, 95% CI	Fishers exact test
					Treatment		
					Age		
					Sex		
					Asthma		
					Eczema		
					Rhinitis		
					Weight		
Logistic regression - adjusted odds of desensitised peanut allergy	2.2	Full analysis	Allergy desensitised or undesensitised	6 months	Sensitisation to tree nuts	odds ratios, 95% CI	Logistic regression
					Peanut specific IgE		
					Peanut SPT wheal diameter		
					Basophil AUC of CD63MFI against peanut protein concentration		
					QoL score		
					Family history of allergy		
					Baseline NOAEL		
Comparison of change in threshold between treatment groups	2.3	Full analysis	Threshold	Baseline and 6 months	Treatment	mean, SD, absolute and fold difference, 95% CI	t-test

Comparison of change in quality of life score between treatment groups	2.4	Full analysis	Quality of life score	Baseline and 6 months	Treatment	median, range, difference, 95% CI	Mann-Whitney U test
Comparison of change in quality of life score before and after intervention within and between treatment groups	2.5	Full analysis	Quality of life score	Baseline and 6 months (immunotherapy) 6 and 12 months (Waiting list)	Treatment	median, range, difference, 95% CI	Wilcoxon sign rank test Mann-Whitney U test

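### The adjusted logistic model is specified in two conflicting ways (20 covariates by Section 7.2, 13 in Table 2.2), and about 46 expected events are too few for either under ordinary maximum likelihood

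*SAP*

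**What the plan says.** Section 9.1 gives two analyses of desensitisation at six months: a Fisher's exact test, and then "Multiple logistic regression will be used to adjust the odds of desensitisation for baseline characteristics described in section 7.2". Section 9.2 uses the same reference to Section 7.2 for the logistic model of the 800 mg response.

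Section 7.2 opens with "The covariates that are recorded at baseline are" and lists 20 single variables. For incomplete covariates, Section 7.3 says "we will include a binary indicator variable for the missingness of each covariate in regression models". No variable selection or penalisation is named.

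Section 13.1, Table 2.2, titled "Logistic regression - adjusted odds of desensitised peanut allergy", lists treatment and 13 covariates. Table 2.8, in all patients who had immunotherapy, repeats those 13. Section 11 and Figures 2.6 and 2.7 draw probability curves from the logistic models.

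Section 5.3 names seven minimisation factors: age, sex, allergy severity, asthma, peanut IgE, challenge threshold "and other current food allergies".

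**The concern.** There are two faults in the adjusted model, and they should be kept apart.

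**Specification and size.** An analyst can follow Section 9.1 or Table 2.2 and will fit different models. Either has few events per term. In that situation maximum-likelihood logistic regression moves the treatment odds ratio away from 1 and gives Wald intervals that are too narrow. Some Section 7.2 variables also overlap heavily: NOAEL and LOAEL come from the same challenge, and the two AUCs from the same basophil assay.

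**Allocation factors.** Allocation was balanced on seven factors. An adjusted analysis would normally include them all, and neither version does.

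At stake is an adjusted odds ratio that sits in the primary efficacy section and will be reported with a 95% interval. Readers may take it as the better effect estimate because it is adjusted.

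**Working it through.** **1. The plan's own figure.** Section 6: "Based on Fisher's exact test with 90% power and 5% significance (two-sided) a sample size of 49 in each group", to detect "desensitisation to peanut of 64% and 30% in the intervention and control group respectively". Exact enumeration of Fisher's test gives power 0.896 at 48 per arm and 0.906 at 49, so 49 is reproduced. Dropout: 49 / 0.95 = 51.6, rounded up to 52, as stated.

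**2. Expected events.** At 49 per arm: 49 × (0.64 + 0.30) = 46.1 events and 98 − 46.1 = 51.9 non-events. At 52 per arm: 52 × 0.94 = 48.9 events. The planning odds ratio is (0.64/0.36) / (0.30/0.70) = 4.15.

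**3. Terms.** Section 7.2: demographics 4, allergic diseases 3, tree nut sensitisation 1, worst-reaction score 1, challenge results 3, skin prick tests 2, IgE 2, basophil AUCs 2, tryptase 1, quality of life 1. That makes 20, or 21 terms with treatment. Table 2.2 has 13, or 14 with treatment.

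| Model | Terms | Events per term, 49 per arm | 52 per arm |
|---|---|---|---|
| Section 7.2 | 21 | 46.1/21 = 2.2 | 48.9/21 = 2.3 |
| Table 2.2 | 14 | 46.1/14 = 3.3 | 48.9/14 = 3.5 |

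Missingness indicators lower these further. If, say, five Section 7.2 covariates had gaps, the figure would be 46.1/26 = 1.8.

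**4. Effect on the odds ratio.** Maximum-likelihood fits were simulated at 49 per arm with 2,000 runs per setting. The conditional odds ratio was set to 4.15, so the inflation shown is not the ordinary gap between conditional and marginal odds ratios. Assumptions not in the SAP: normal covariates; none prognostic, or three with log odds ratio 0.5 per SD; correlation 0 or 0.3. Ranges run over these settings.

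| Covariates | Median OR | Bias in log OR | 95% CI coverage |
|---|---|---|---|
| 3 | 4.4–4.5 | +6% to +7% | 0.94–0.95 |
| 7 | 4.8–4.9 | +12% to +14% | about 0.94 |
| 13 | 5.5–5.7 | +22% to +26% | 0.90–0.91 |
| 20 | 6.7–7.4 | +39% to +49% | 0.85–0.86 |

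With no treatment effect (uncorrelated covariates, three prognostic) the adjusted test rejects in 5.3%, 7.2% and 8.6% of runs for 3, 13 and 20 covariates. At 52 per arm, 20 covariates still give a median of 6.3–7.1.

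**5. Minimisation factors.**

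| Factor (Section 5.3) | Section 7.2 | Table 2.2 |
|---|---|---|
| Age, sex, asthma, peanut IgE | yes | yes |
| Challenge threshold | yes (NOAEL, LOAEL) | yes (NOAEL) |
| Allergy severity | yes (worst-reaction WAO score) | no |
| Other current food allergies | no | no |

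Section 7.2 covers six of seven and Table 2.2 five. Tree nut sensitisation, in both, is only a partial proxy for the missing food allergy factor. Table 1.1 lists other food allergy, so it is collected.

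**6. Table 2.8.** The SAP gives no rate for the 800 mg response. As an illustration, take 49 + 35 = 84 treated patients and assume that 64% are desensitised in both groups. Anyone tolerating 1400 mg also meets the 800 mg definition, so non-responders number at most 0.36 × 84 = 30.2. That is 30.2/14 = 2.2 of the scarcer outcome per term.

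**7. Candidate remedy.** The seven factors, with their categories as dummies, need 1 + 1 + 3 + 1 + 1 + 2 + 1 = 10 terms, or 11 with treatment: 46.1/11 = 4.2 events per term. Simulated with 10 covariate terms, maximum likelihood still gives a median of 5.0 to 5.4. Firth gives 4.2 with coverage 96–97%.

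**The case against.** **The primary comparison is safe.** Fisher's exact test is listed first, sizes the trial and has its own table. This stands. A reader might infer from the placement in Section 9.1 that the primary conclusion is at risk. The documents do not support that.

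**Section 7.2 may be only a pool.** It is introduced as what is recorded at baseline, and Table 2.2 names the model's terms. That is a natural reading, and it brings the expected inflation down to the 13-covariate row. But Section 9.1 refers to Section 7.2 without restriction, and the shorter model is still biased.

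**Missing allocation factors do not cause the inflation.** It is tempting to link the two faults. Omitting a prognostic factor from a logistic model tends to pull the odds ratio towards 1; the number of terms does the inflating. Nor does either model leave out the factors wholesale.

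**The reach is limited.** Section 9.2 also allows a linear regression of threshold on the Section 7.2 covariates. Events per term do not apply there: a check of least squares with 20 covariates and 98 patients gave an unbiased treatment effect with 95% coverage. Much larger inflation can be produced by assuming a control rate near 10%, but the SAP plans 30%.

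**A short list is not needed to remove the bias.** Firth gave a median of 4.2 with all 20 covariates and 4.1 with 13, with coverage 96–97% and 96%. This stands too. The case for shortening the list is that the two specifications must be reconciled and the allocation factors included.

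**Conclusion.** The point holds for the adjusted logistic analyses only. The SAP specifies two different models for one analysis, which needs no simulation to see. Fitted by ordinary maximum likelihood, both are overfitted: a median odds ratio of about 7 (coverage about 85%) or about 5.5 (about 91%) against a true 4.15. The event counts rest on the planning rates. The size of the inflation also rests on the assumed covariate structure and an unpenalised fit, and will differ in the real data; its direction was the same in every setting tried.

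As a separate and smaller gap, one allocation factor is missing from both models and a second from Table 2.2. The adjusted odds ratios for desensitisation and the 800 mg response, Table 2.8 and the probability curves are affected. The Fisher's exact test and the linear threshold model are not.

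**What to change.** - In Section 9.1 and in the logistic model of Section 9.2, replace the reference to Section 7.2 by one pre-specified list: treatment plus age, sex, allergy severity, asthma, peanut IgE, challenge threshold and other current food allergies. State the form in which each enters.
- Fit by Firth penalised likelihood with profile-likelihood 95% intervals.
- Make Table 2.2 match, and draw Figures 2.6 and 2.7 from the revised models.
- Label the wider covariate model in Table 2.8 exploratory and fit it with penalisation.

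The cost is SAP wording and one table shell. No new data are needed: the factors were used for allocation, so they should be complete and need few or no missingness indicators. The downside is that odds ratios for the dropped covariates no longer appear in the adjusted primary model.
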